PRAGMA-CF	Perth-Rotterdam Annotated Grid Morphometric Analysis for CF					
PBS	Phosphate Buffered Saline					
QALY	Quality-Adjusted Life-Years					
RV	Residual Volume					
GST	Guy's and St Thomas' NHS Foundation Trust					
SHIELD CF	Study of Host Immunity and Early Lung Disease in CF					
TLC	Total Lung Capacity					
WOCBP	Women of Childbearing Potential					

HYPOTHESIS AND SPECIFIC AIMS FOR PARENT STUDY

Hypothesis

- a. Use of ETI in routine clinical practice is associated with significant and sustained improvements in airway, liver and gastrointestinal outcomes and quality of life in children and adults with cystic fibrosis.
- b. Adherence to routine therapies will decrease after initiation of ETI

Specific Aims

- 1. To determine the effect of treatment with ETI on pulmonary function (FEV1 and LCI) in children and adults with CF over a period of 2 years.
- 2. To determine the effect of treatment with ETI on spirometry-controlled CT scores in children and adults with CF over a two-year period.
- 3. To determine the effect of treatment with ETI on airway infection and inflammation in children and adults with CF
- 4. To determine the effect of treatment with ETI on nutrition, gastrointestinal symptoms, gut inflammation and pancreatic function in children and adults with CF over a two-year period
- 5. To determine the effect of treatment with ETI on CF liver disease in children and adults with CF over a two-year period.
- 6. To determine the effect of treatment with ETI on antibiotic treatment of pulmonary disease in children and adults with CF over a two-year period
- 7. To assess the impact of the introduction of ETI on adherence with overall medical treatments for CF

HYPOTHESIS AND SPECIFIC AIMS FOR EXTENSION STUDY

Hypothesis

a. Use of ETI in routine clinical practice is associated with significant and sustained improvements in airway, liver and gastrointestinal outcomes and quality of life in children and adults with cystic fibrosis.

Specific Aims

- 1. To determine the longitudinal effect of ETI on pulmonary function (FEV1 and LCI) in children and adults with CF over an additional period of 5 years.
- 2. To determine the longitudinal effect of ETI on spirometry-controlled CT scores in children and adults with CF over an additional period of 5 years
- 3. To determine the effect of treatment with ETI on airway infection and inflammation in children and adults with CF.

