The triple combination modulator compound Elexacaftor/Tezacaftor/Ivacaftor (ETI), however, is associated with significant improvements in sweat chloride, nutrition and pulmonary disease in children aged 6 years and above with one or more Phe508del mutation(61-64) and is now approved for use in many jurisdictions. Ivacaftor and ETI are considered highly effective modulator therapy (HEMT) on the basis of their very significant impact on sweat chloride levels and end organ function. In longer term studies of Ivacaftor, the significant initial improvement in pulmonary function has returned to baseline after approximately 3-5 years of treatment (65,66), with data from the Irish registry suggesting that the pulmonary function trajectory after initial treatment gains is heavily influenced by age (worse in older subjects with more advanced disease)(67). Longer term data is not available yet for ETI. The availability of these medicines for a large proportion of our patients represents both a fantastic advance in our efforts to manage our patients effectively but also a truly 'disruptive' event in the history of clinical management of CF. It is vital that we seek to understand the impact of this across several different clinical and non-clinical spheres by collecting a wide range of outcome measures on a large group of individuals and following them over many years.

Clinical Outcome Measures in CF

Traditional outcome measures for clinical trials of new therapies in CF have focused on manifestations of more advanced disease such as FEV1, nutritional indices, survival and exacerbations(68). These outcome measures have been of use in individuals with advanced disease, low lung function and poor nutrition. In children (and many adults) who may have better preserved pulmonary function and nutrition more novel outcome measures are required, and increasingly used in the CF community.

Multiple Breath Washout

Most children in the 6-11 year old bracket, and many in the 12-16 year old group, have normal FEV1 values (CFRI annual report 2016) despite the finding that more than 50% of children with CF have evidence on CT scanning of structural lung damage in the form of bronchiectasis by school age(6) which is usually progressive and non-reversible(7). Multiple Breath Washout (MBW) is an effort independent non-invasive technique performed on spontaneously breathing individuals, which measures ventilation inhomogeneity. MBW involves

P.I. [name]

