and highlighting the need for more sensitive outcome measures in this group. Baseline (n=78) and 1 year (n=65) spirometry-controlled CT scans have been analysed and will be presented at ECFS and published shortly. Table 4 below summarises the PRAGMA scores analysed to date (unpublished). Table 3 outlines the key available data currently from the first phase of RECOVER showing significant improvements in all measured indices over 6 and 12 months. Over 6 months of ETI use, global CF Abd scores improved significantly from 15.0 \pm 1.4 to 10.7 \pm 1.1; p<0.0001, with significant improvements in sub-scores for domains of 'pain', 'GERD', 'impairment of quality of life' and 'appetite' but not 'disorders of bowel movement'.

	В	aseline (N	=114)		6 m (N=1	03) 12 m (N=90)		BL v all FU	BL v 6m	6m v 12m		
	N	Mean	Std Dev	N	Mean	Std Dev	N	Mean	Std Dev	p-value	p-value	p-value
Sweat Chloride	107	85.78	18.054	94	44.92	18.886	80	44.23	18.936	<.0001	<.0001	0.7358
LCI	82	12.21	3.829	83	10.14	3.689	49	9.85	4.274	<.0001	<.0001	0.3187
pp FEV1	114	83.65	15.399	82	91.73	16.032	87	92.11	16.319	<.0001	<.0001	0.7356
Weight z score	114	0.07	0.812	103	0.32	0.790	90	0.27	0.827	<.0001	<.0001	0.1253
BMI z score	114	0.12	0.819	103	0.36	0.792	90	0.28	0.863	<.0001	<.0001	0.0484
FeNO	112	13.59	10.407	103	16.30	12.397	90	15.96	12.397	0.0118	0.0192	0.7827
CFQR-RD	37	83.32	15.212	27	97.20	7.508	22	95.49	8.792	<.0001	<.0001	0.4386

 Table 3. Available cleaned data from people with CF aged 12 and over and one or more copies of

 F508del from the RECOVER study.

	All Participants						
	Baseline (N=85)			12 months (N=64)			Baseline v 12 mths
Variable	Ν	Mean	Std Error	Ν	Mean	Std Error	p-value
% Bronchiectasis	85	3.86	0.428	64	3.29	0.388	0.3256
% Disease	85	7.34	0.697	64	3.98	0.406	0.0001
% Trapped Air	85	20.61	1.606	63	11.48	1.749	0.0002
% Mucous plugging	85	2.22	0.351	64	0.11	0.042	<.0001
% Bronchial Wall Thickening	85	1.21	0.114	64	0.55	0.070	<.0001
	F508del/F508del						
	Baseline (N=55)			12 months (N=41)			Baseline v 12 mths
Variable	N	Mean	Std Error	N	Mean	Std Error	p-value
% Bronchiectasis	55	3.27	0.449	41	2.49	0.365	0.1769
% Disease	55	5.64	0.738	41	3.09	0.396	0.0030
% Trapped Air	55	13.90	1.790	41	9.01	1.666	0.0485
% Mucous plugging	55	1.35	0.335	41	0.07	0.033	0.0003
% Bronchial Wall Thickening	55	0.98	0.110	41	0.52	0.080	0.0010
	F508del/Minimum function						
	Baseline (N=30)			12 months (N=23)			Baseline v 12 mths

	(N=30)			(N=23)			v 12 mths

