FEV1 measured by spirometry is the most widely used evaluation of lung function in CF. As FEV1 has been used as the primary endpoint in numerous clinical trials in CF to date, it is important that the rate of FEV1 change is recorded and analyzed as a secondary endpoint in this study. Spirometry will be carried out on each subject at three monthly intervals throughout the duration of the parent study, and annually during the extension study as part of routine clinical care. Spirometry will be performed according to the American Thoracic Society (ATS) guidelines(125). Spirometry values collected as part of routine clinical care will be used for this study, rather than repeating this testing specifically for the purposes of the study. Other spirometric measures such as FVC, FEV1/FVC and FEF25-75 will be collected for inclusion in later analyses. The absolute and relative changes and rate of change in % predicted FEV1 (GLI – Global Lung Initiative) will be assessed from baseline to annual subsequent follow up periods.

Lung Clearance Index

LCI will be performed with the Exhalyzer D multiple breath washout device (Eco Medics AG, Duernten, Switzerland). The test itself is usually completed within twenty to thirty minutes (the test takes longer the more airway disease is present) and will be performed according to the European Respiratory Society / American Thoracic Society consensus statement 2013 on the performance of multiple breath inert gas washout(126).. MBW operators will be trained and certified by the team at Guy's and St Thomas' NHS Foundation Trust) under the supervision of [name]. Centralized over-reading will be completed at the RBH centre. All tests will be performed in replicate, and average values calculated for acceptable trials. LCI will be performed pre-bronchodilator in all subjects. LCI will be performed three months prior to the baseline visit and then at baseline and at 6 monthly intervals subsequently for the parent study, and annually during the extension study..

Analysis plan

The primary endpoint for LCI for the parent study will be the absolute difference in LCI in children on ETI compared the pre-treatment baseline. An interim analysis will be completed after one year of treatment, and a final parent study analysis at the end of two years. Subsequent annual and multi-annual change in LCI will be assessed during the extension study.

Risks with FEV1 and LCI Data Collection

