Eligibility Assessment	Х	Х															
Sweat Chloride		Х				Х		Х				Х	Х	х	Х	х	Х
LCI	Х	Х				Х		Х		Х		Х	Х	Х	Х	Х	Х
Spirometry-controlled CT (A*)		Х						Х				Х		X1		X1	
Height/Weight/BMI*	Х	Х			Х	Х	Х	Х	Х	Х	Х	Х	Х	Х	Х	Х	Х
FEV1*	Х	Х			х	Х	Х	х	Х	Х	Х	Х	Х	х	х	Х	Х
Airway Sampling (Micro)*	Х	Х			Х	Х	Х	Х	Х	Х	Х	Х	Х	Х	Х	Х	Х
Nasal Lavage (A*)		Х				Х		Х				Х	Х	х	х	Х	Х
FeNO	Х	Х				Х		Х									
Liver Function Testing*		Х			Х	Х	Х	Х				Х	Х	х	Х	Х	Х
Liver Ultrasound		Х						Х				Х	Х	Х	Х	Х	Х
Sputum Collection (A*)		Х				Х		Х		Х		Х	Х	х	Х	Х	Х
Liver Examination		Х						Х				Х					
Stool Collection		Х	Х			Х						Х	Х	х	Х	Х	Х
Blood Collection		Х						Х				Х	Х	Х	Х	Х	Х
Breath Sample Collection		Х			Х	Х	Х	Х									
Abdominal Symptom Score	Х	Х	Х	Х		Х		Х				Х	Х	х	Х	Х	Х
CFQ-R		Х				Х		Х				Х	Х	Х	Х	Х	Х
Pharmacy Records MPR								Х				Х					
Adherence Questionnaire	Х	Х			Х	Х	Х	Х	Х	Х	Х	Х					
MEMs Caps Reading (M)								Х				Х					
Antibiotic Use		Х						Х				Х					
Adverse Event Check			Х	Х	Х	Х	Х	Х	Х	Х	Х	Х	Х	Х	Х	Х	Х
Mental Health Questionnaire													Х	Х	Х	Х	Х

* Collected as normal clinical care,

A - Advanced arm testing in RECOVER parent study

¹ Only for patients who performed spirometry-controlled CT in parent study. Scan at years four and six at sites doing routine clinical CT. Scan at year six for sites not performing biennial CT

M - MEMs study only

Table 14. Schedule of assessments. Each visit has a study window. For the RECOVER parent study the baseline visit (0 month visit) will have an 8 week pre commencement on ETI start window. The 1, 2 and 3 month visits have +/- 2 week window. The 6, 9, 12, 15, 18, 21 and 24 month visits have +/- 1 month window. For the RECOVER extension study each annual visit will have a window of +/- 4 month.

Study Governance and Management Plan

RECOVER

[figure not shown]

Figure 6 RECOVER study management structure.

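### The FEV1 rate of change is anchored at the pre-ETI baseline, so the early gain on ETI is mixed into the rate and it does not describe the course on established treatment

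*Protocol*

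**What the plan says.** The protocol, under Specific Aim 1 (Forced Expiratory Volume in 1 second), states that "it is important that the rate of FEV1 change is recorded and analyzed as a secondary endpoint in this study". The same paragraph sets the start point in one sentence covering absolute change, relative change and rate: the "rate of change in % predicted FEV1 (GLI – Global Lung Initiative) will be assessed from baseline to annual subsequent follow up periods". Spirometry is done "at three monthly intervals throughout the duration of the parent study, and annually during the extension study".

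The note to Table 14 (Study Visit Timetable) places the starting value before treatment: "the baseline visit (0 month visit) will have an 8 week pre commencement on ETI start window".

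Extension Aim 1 is "To determine the longitudinal effect of ETI on pulmonary function (FEV1 and LCI) in children and adults with CF over an additional period"; that period is five years. The hypothesis is that improvement is sustained. The background section on CFTR modulators reports that in longer-term ivacaftor studies "the significant initial improvement in pulmonary function has returned to baseline after approximately 3-5 years of treatment". It adds, from Irish registry data, that "the pulmonary function trajectory after initial treatment gains is heavily influenced by age". The background thus treats the initial gain and the later course as two separate things. The endpoint sentence does not.

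**The concern.** ETI produces a quick rise in FEV1, and the longer-term question is what happens afterwards. A rate that starts before treatment adds the rise to the later change and spreads the sum over the elapsed time. Two things follow. The figure shrinks as follow-up lengthens even if lung function is constant, so rates at years 2, 4 and 7 are not comparable with one another. In the parent study it can also be positive while lung function on established ETI is falling. The question of sustained benefit rests on the slope after the gain, which this endpoint does not isolate.

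**Working it through.** The protocol states no design figure for FEV1, so there is none to reproduce. The check is arithmetic on its own means.

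**Inputs.** Table 3 (12+ cohort) gives mean ppFEV1 of 83.65 at baseline (n=114), 91.73 at 6 months (n=82) and 92.11 at 12 months (n=87), with 6 v 12 months p=0.7356. The schedule is 3-monthly to month 24, then annual to year 7. The later loss *d* in points/year is an assumption. The protocol says that longer-term ETI data do not yet exist.

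**The step.** J = 91.73 − 83.65 = 8.08 points. Total change at 12 months is 92.11 − 83.65 = 8.46, so 8.08/8.46 = 96% of the year-1 rate from baseline is the step. From month 6 to month 12 the change is 0.38 points, or 0.38/0.5 = +0.76 points/year.

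**Two-point rate from baseline at year T**, with the gain complete at month 6 and a linear loss afterwards:

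R(T) = (J − d(T − 0.5)) / T

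- d=0: 8.08/2 = +4.04 at year 2; 8.08/7 = +1.15 at year 7.
- d=1: (8.08 − 1.5)/2 = +3.29 at year 2; (8.08 − 6.5)/7 = +0.23 at year 7.
- d=2: (8.08 − 3.0)/2 = +2.54 at year 2; (8.08 − 13.0)/7 = −0.70 at year 7.

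R(T) reaches zero at T = 0.5 + J/d: year 8.58 for d=1 and year 4.54 for d=2. At year 2 it is positive for any loss below 8.08/1.5 = 5.39 points/year.

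**Fitted line.** The protocol does not say whether the rate is a two-point difference or a regression slope, so a least-squares line through all scheduled visits from month 0 was also computed. The gain rises linearly and is complete at month 3 or at month 6, with the loss starting then. Ranges cover the two timings.

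| Assumed later loss (points/year) | Method | Year 2 | Year 4 | Year 5 | Year 7 |
|---|---|---|---|---|---|
| 0 | two-point | +4.04 | +2.02 | +1.62 | +1.15 |
| 0 | fitted | +2.15 to +2.96 | +0.81 to +1.15 | +0.54 to +0.78 | +0.30 to +0.44 |
| 1 | two-point | +3.29 | +1.15 | +0.72 | +0.23 |
| 1 | fitted | +1.22 to +2.15 | −0.16 to +0.22 | −0.44 to −0.18 | −0.69 to −0.54 |
| 2 | two-point | +2.54 | +0.27 | −0.18 | −0.70 |
| 2 | fitted | +0.29 to +1.33 | −1.14 to −0.71 | −1.42 to −1.13 | −1.68 to −1.51 |

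In an extreme timing, with no gain visible at month 3 and all of it at month 6, the fitted year-2 values rise to +3.77, +2.95 and +2.14 for losses of 0, 1 and 2. The year-5 value for a loss of 1 is then about zero (+0.06).

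**Link to the ivacaftor course.** If the 8.08-point gain were lost by year 3 or year 5, the implied loss would be 8.08/2.5 = 3.23 or 8.08/4.5 = 1.80 points/year. The two-point rate at year 2 would then be +1.62 or +2.69. A fitted line at 3.2 points/year gives −0.83 to +0.35, so at that speed the sign may already be right.

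**After the fix.** Under the same model, a slope from month 6 over visits 6 to 24 returns −1.0 and −2.0 for losses of 1 and 2. With no loss it is zero by construction.

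**The case against.** The strongest reply is that one phrase covers three quantities and may only describe the assessment window. No formula is given. The Statistical Analysis section plans linear mixed models and names slopes, pre/post analysis and response trajectory, which is compatible with a step plus a slope. Annual absolute changes are also planned, so a fall between years can be read by subtraction. Table 3 itself already tests baseline v 6 months and 6 v 12 months separately.

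Much of this stands as mitigation. The general text leaves room for the right model, and a fall would not be hidden from a reader who compares annual changes. But the general text gives no start time for the slope and does not override the specific sentence. That sentence sets the start at baseline, and both the two-point rate and a single fitted line from there absorb the step.

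A reader might go further and infer that a patient losing lung function will be reported as improving for years. The documents do not support that. It depends on the two-point formula, which the protocol does not state. With a fitted line and a loss of 1 to 2 points/year, the rate is negative by about year 4 to 5. It also needs a gain that has not yet been cancelled, and a patient with no gain is unaffected. The loss rates are assumptions, since Table 3 shows a plateau to 12 months.

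**Conclusion.** The concern holds as a defect in how one secondary endpoint is anchored. The part that needs no assumption about decline is enough: with stable lung function after the step, the two-point rate falls from +4.04 to +1.15 points/year between years 2 and 7 (fitted line about +2.2 to +3.0, falling to +0.3 to +0.4). With an assumed loss of 1 to 2 points/year, the year-2 rate is positive by either method. Later in the extension the problem is mainly understatement: at year 7 a fitted line shows −0.69 to −0.54 for a true −1, and −1.68 to −1.51 for a true −2. The two-point rate turns negative at about year 4.5 for a loss of 2, and not by year 7 for a loss of 1.

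The size rests on a difference of group means with differing n, from the 12+ cohort only, on a gain complete by month 3 or 6, and on a linear later course. Another gain would rescale the no-decline figures in proportion.

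**What to change.** Keep absolute and relative change in ppFEV1 from baseline to each annual visit as stated. Separate the rate of change from that sentence and define two quantities:

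- **Initial response:** change from the pre-ETI baseline to a fixed early on-treatment visit, for example month 6.
- **Rate of change on ETI:** the slope from that visit onward, for example through a step and a separate on-treatment slope in the linear mixed model already planned. Vary the change point in a sensitivity analysis.

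A comparison with each participant's pre-ETI slope from registry data is optional, where consent and data allow.

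The cost is a wording change and extra model terms. FEV1 is already collected 3-monthly and then annually, so no visit is added. The downside is that the reported slope will look less favourable than the rate from baseline.

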Sputum samples will be collected and stored on all participants annually, and these samples will be used for collaborative projects, however detailed analysis of these specimens will not be part of the extension study.

Sputum processing

As part of standard clinical care, sputum or oropharyngeal specimens (OPS) will be collected and processed in clinical laboratories. This data will be stored on local hospital systems and uploaded in the usual way from each center to the relevant national registry, our collaborators in this study. Separate to this, sputum samples for research purposes will be collected at study visits and immediately processed in the laboratory. Measurement of markers of inflammation in sputum is greatly facilitated by having a detailed and reproducible protocol for processing of fresh sputum specimens after collection. We will use such a system to ensure that our samples are collected, handled and processed to the highest level of quality during the study (138). Briefly, according to the TETRIS protocol, sputum will be collected from subjects, either spontaneously or after hypertonic saline induction, and immediately placed on ice for transport to the laboratory. The two-step temperature controlled process will be followed according to the protocol, however, once sputum plugs have been homogenized with cold phosphate buffered saline (PBS), and prior to centrifugation, an aliquot of this homogenized sputum will be mixed with an RNA preservative (RNAlater) and frozen at -80°C for later 16s shotgun sequencing. Sputum supernatant, once processed by TETRIS, will be aliquoted and stored at -80°C.

If a subject is not in a position to produce sputum, the research nurse/coordinator will arrange for sputum induction to be carried out. Sputum induction will be performed by using 7% hypertonic sodium chloride solution will be nebulized for 15 minutes with the subject encouraged to carry out airway clearance maneuvers during and after nebulization. All sputum collected over a 30-minute period will be utilized.

Nasal Lavage

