Nasal lavage will be collected as previously described(21) at baseline, 6 months and one year. Briefly, 10ml of sterile isotonic saline will be slowly injected into each nostril sequentially using a 10ml syringe while the subject occludes their soft palate and reclines their head. The saline is allowed to remain in the nasal airways for 10 seconds before being drained into a sterile collection container by the subject leaning forward. If a clinical specimen is required, 5ml of fluid will be sent separately to the local microbiology lab for routine processing. Lavage fluid will be put on ice and transferred to the laboratory for aliquoting and immediate freezing at -80°C. An aliquot of the nasal lavage fluid will be mixed with an RNA preservative (RNAlater) and frozen at -80°C for later 16s shotgun sequencing. Nasal lavage will be performed in individuals 12 years and older.

Airway Infection

Microbiological processing of samples will be completed as per usual clinical practice at clinical microbiology labs at each clinical site. As part of the study, consent will be sought from parents to access historic and current clinical microbiology sample results uploaded to CFRI and the UK CF Registry. Using a similar approach to national registries we will track the percentage of individuals culturing positive for particular organisms prior to and over the course of the study period. In addition, we will analyse trends at an individual level prior to and during treatment with ETI. We will be able to compare pulmonary function and imaging findings collected via RECOVER to clinically collected airway infection data.

Microbiome Analysis

DNA extraction and processing will be performed by our collaborators at the APC Microbiome Ireland in Cork, Ireland who have extensive experience with gut and lung microbiome projects in CF(139-141). Samples will undergo deep shotgun sequencing using the Illumina NextSeq platform. Detailed descriptions of microbial community composition and metabolic profile will be obtained.

Breath Sample Collection

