The main foreseeable risk factor in this part of the study is the inability to collect a sputum specimen. Many patients, especially younger or healthier ones may not routinely produce sputum on a regular basis. We further suspect that, in light of the significant improvements in clinical outcomes demonstrated already for Kaftrio, that many individuals will go from being sputum producers to non-producers on treatment. We will work closely with the clinical teams to ensure that sputum specimens are optimized in terms of the split between laboratory and research processing. Each clinic has their own mechanism for trying to facilitate sputum production either at clinics or annual assessment – we will work with teams to ensure that saline induction, where used, can be facilitated by the research team to try to ensure a suitable sample sputum volume can be collected for all uses. We are aiming to collect 4 sputum samples over 2 years for RECOVER, with the baseline and year one samples prioritized. Where possible the research team will work with the subjects and clinical teams to ensure that all efforts are made to obtain a sufficient sample volume at these timepoints in particular, including sputum induction. The use of the TETRIS sputum processing protocol will mean that it is acceptable to use

P.I. [name] spontaneously produced and induced sputum interchangeably when obtaining samples. This will greatly facilitate optimal sampling.

We expect that an incomplete set of samples will be collected and have factored this into our study calculations in terms of numbers and budget. With a recruitment of 150 individuals to the advanced group we would ideally expect 600 sputum samples and 414 nasal lavage samples to process (1014 total). In reality we estimate that it is likely that we will have 90% of individuals produce one sputum sample, 80% to produce 2 samples, and 70% to produce 3 samples and 60% to produce 4 samples. We estimate that 80% of eligible individuals will produce one nasal lavage sample, 70% two samples and 60% three samples. The main foreseeable risk factor with nasal lavage is aspiration of isotonic saline. In practice this is a very similar procedure to sinus rinse which is commonly performed by many people with CF on a daily basis where we see almost no adverse effects in those who learn how to do the procedure. It is likely that some people may find this an uncomfortable or awkward procedure and elect not to do it.

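### Airway infection is measured as percent culture-positive without regard to specimen type, although the protocol expects sputum production to fall on ETI, so specimen type is confounded with treatment period

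*Protocol*

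**What the plan says.** Under Specific Aim 3, the Airway Infection section of the protocol defines the measure: "we will track the percentage of individuals culturing positive for particular organisms prior to and over the course of the study period". The next sentence adds a within-person version: "In addition, we will analyse trends at an individual level prior to and during treatment with ETI". The data are not study cultures. Consent is sought to "access historic and current clinical microbiology sample results uploaded to CFRI and the UK CF Registry", and Table 14 marks airway sampling for microbiology as normal clinical care.

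The Sputum processing section says what feeds those results: "As part of standard clinical care, sputum or oropharyngeal specimens (OPS) will be collected and processed in clinical laboratories". Either specimen counts.

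The section on risks in airway inflammation data collection then predicts "many individuals will go from being sputum producers to non-producers on treatment". There it is treated as a shortage of research sputum for inflammatory markers and nitric oxide metabolites, and no link is drawn to the culture measure.

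Airway microbial culture is a listed secondary outcome. The Statistical Analysis section names demographic and co-morbidity covariates for its models and does not mention specimen type.

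**The concern.** The measure compares the same people before and during ETI, and no comparison group is described for cultures. Such a comparison can be read as a change in infection only if the means of detecting infection stays the same. The protocol itself predicts that it will not: some people who gave sputum before ETI will have something else cultured on ETI, or nothing.

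If sputum and throat specimens differ in how often they grow a given organism, percent positive will move when the specimen mix moves, even with infection unchanged. The individual-level trends are exposed in the same way, because one person's series may switch specimen when treatment starts. The culture data are also to be related to lung function and imaging, so the misclassification would carry into those analyses. At stake is whether the infection half of Aim 3 can be interpreted as infection.

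**Working it through.** The protocol gives no expected rate, change or power for culture positivity, so there is no figure to reproduce. The calculation below illustrates the mechanism.

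**Inputs from the protocol**
- Either specimen feeds the measure (Sputum processing).
- The measure makes no reference to specimen type (Airway Infection).
- The sputum share is expected to fall on ETI, with no percentage given (Risks in Airway Inflammation data collection).
- The projected cohort is 254, of whom 117 are aged 6-11 and 137 are 12 or older (Table 6).

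**Assumed inputs, not in the documents**
- True carriage P = 40%, unchanged.
- Sputum sensitivity 90%.
- Throat-specimen sensitivity s from 40% to 90%.
- Sputum share f of cultures falling from 80% to 40%.

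**Formula.** Observed positivity = P × [f × 0.90 + (1 − f) × s]. The artefact is the before-minus-after difference, P × (fall in f) × (0.90 − s) = 0.40 × 0.40 × (0.90 − s) = 0.16 × (0.90 − s).

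| s | Before: 0.40 × (0.72 + 0.20s) | On ETI: 0.40 × (0.36 + 0.60s) | Apparent fall | Relative fall |
|---|---|---|---|---|
| 40% | 32.0% | 24.0% | 8.0 points | 25% |
| 50% | 32.8% | 26.4% | 6.4 points | 20% |
| 70% | 34.4% | 31.2% | 3.2 points | 9% |
| 90% | 36.0% | 36.0% | 0 | 0% |

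**Wider grid.** With carriage of 30% or 50%, s from 50% to 90%, and sputum share falling 90% to 60%, 80% to 40% or 70% to 20%, the apparent fall runs from 0 to 10 points (0% to 26% relative).

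**Direction can reverse.** With sputum sensitivity 80%, throat sensitivity 90%, carriage 50% and sputum share 90% to 60%:
- before: 0.50 × (0.72 + 0.09) = 40.5%
- on ETI: 0.50 × (0.48 + 0.36) = 42.0%

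That is an apparent rise of 1.5 points.

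**Dilution by the younger cohort.** Suppose all 6-11 year olds give throat specimens throughout, carriage is equal across ages, and the 80% to 40% shift applies only to those aged 12 or older. The artefact is then multiplied by 137/254 = 0.539: 8.0 points becomes 4.3, and 6.4 becomes 3.5.

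In this model the artefact is zero within a single specimen type, whatever values are assumed.

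**The case against.** **Direction.** A reader might infer that the bias must flatter ETI and look like pathogen clearance. The documents do not support that. It requires throat specimens to have lower yield, organism by organism, and no yields are given. At equal yield there is no artefact; at higher throat yield it runs the other way. This objection stands, and it limits the point to possible confounding of unknown sign and size.

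**Sputum induction.** The protocol arranges induction for people who cannot produce sputum and hopes it will yield enough volume for all uses. This may soften the shift but does not remove it. Research sputum is collected separately from the clinical cultures and, in the parent study, only in the advanced group; 87 participants are projected for standard testing (Table 6). Spontaneous and induced sputum are declared interchangeable, but throat specimens are not included in that statement.

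**Number of cultures.** Table 14 goes from three-monthly sampling to annual, so a reader might infer that percent positive falls simply because fewer tests are done. The Airway Infection section sets no yearly window, and the data are routine clinical cultures whose frequency the visit table does not fix. If Table 14 did govern, there would be two cultures before ETI (months −3 and 0) and four in year one. For a constant carrier detected by 60% of independent cultures (assumed), the chance of any positive would be 1 − 0.4² = 84% before and 1 − 0.4⁴ = 97% after, which runs against ETI. The argument is not sustained.

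**Nasal lavage.** The Nasal Lavage section says "If a clinical specimen is required, 5ml of fluid will be sent separately to the local microbiology lab", and a reader might infer that these cultures contaminate the measure. Nothing says they count towards it, and if they did they would add positives.

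**Left to the SAP.** Stratification and covariates are commonly settled there, and the SAP is not shown. That is fair as to the model. But an SAP can stratify only if specimen type arrives with each result, and the protocol does not say that it will.

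**Conclusion.** The point holds as confounding of specimen type with treatment period. It rests on three statements in the protocol: either specimen is cultured, the measure ignores which, and sputum production is expected to fall on ETI. It needs no assumption about yields.

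Size and direction do depend on assumptions. Under constant 40% carriage, 90% sputum sensitivity and a sputum share falling from 80% to 40%, the apparent fall is between 0 points (equal yield) and 8 points (throat sensitivity 40%), and less if many younger children give throat specimens throughout. The documents cannot say where in that range, or outside it, the study will fall.

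This is one of about 20 secondary outcomes, so the matter is a cheap improvement rather than a threat to the study. It does affect what a before/after change in culture positivity can be taken to mean.

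**What to change.** - Obtain specimen type (sputum, induced sputum, oropharyngeal, other) with every clinical culture result, historic and current.
- Report before/after positivity by specimen type, with the number of cultures of each type in each period.
- Analyse positivity per culture, with specimen type in the model and repeated cultures within person allowed for.
- Give the within-person, same-specimen contrast as a supporting analysis, not the headline. Its sputum part keeps only people who still produce sputum on ETI, a characteristic that treatment may itself have changed, and the report should say so. The by-type results need the same caution, since the people giving sputum on ETI may differ from those who gave it before.

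**Cost.** One extra data field and some analysis wording; clinical sampling does not change. The field may be incomplete for historic registry results, so the share with unknown specimen type should be reported. Intervals within each specimen type will be wider than for the pooled percentage.
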